8.1.1.1 Hypotheses

Let P be the proportion of Treatment Subjects and Attempt Subjects with one or more CSAEs through the Day 90 Assessment and PG be the performance goal, the following hypothesis will be tested in a one-sided test at 0.025 significance level.

- $H_0: P \geq PG$
- $H_A: P < PG$

Where $PG = 12\%$.

8.1.1.2 Sample Size

The sample size estimate was obtained using the binomial exact method. The following assumptions were used in the sample size calculation:

Table 8.1-2: Assumptions for the Primary Safety Endpoint Sample Size Estimate

Assumptions	Primary Safety Endpoint
Expected rate	6%
Performance goal	12%
Attrition	5%
Significance level (one-sided)	0.025
Power	88%
Evaluable subjects	245
Subjects accounting for attrition	258

Under the method and assumption outlined above, the required sample size for this endpoint after attrition is 245, so a minimum of 258 Treatment Subjects are required for the analysis of primary safety endpoint. In addition, all Attempt Subjects will be included in the primary safety endpoint analysis.

8.1.1.3 Statistical Methods

The proportion of Treatment Subjects and Attempt Subjects with one or more CSAEs will be estimated using the Kaplan-Meier method. The 97.5% one-sided upper confidence limit of the observed event rate will be compared to the performance goal of 12%. If the upper confidence limit is less than the performance goal, the null hypothesis will be rejected. The upper confidence limit will be calculated as the pointwise confidence limit using the log-log methodology.

Subjects who withdraw from the study prior to the Day 90 Assessment without experiencing a primary endpoint event will be censored on the date of withdrawal. Subjects who undergo a re-ablation procedure using a commercially available ablation catheter before the Day 90 Assessment without experiencing a primary endpoint event will be censored as of the date of that re-ablation procedure. Subjects who are determined to be Severe COVID-19 Subjects during trial participation without experiencing a primary endpoint event will be censored as of the Onset Date of the condition.

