8.1.1.3 Statistical Methods

The proportion of Treatment Subjects and Attempt Subjects with one or more CSAEs will be estimated using the Kaplan-Meier method. The 97.5% one-sided upper confidence limit of the observed event rate will be compared to the performance goal of 12%. If the upper confidence limit is less than the performance goal, the null hypothesis will be rejected. The upper confidence limit will be calculated as the pointwise confidence limit using the log-log methodology.

Subjects who withdraw from the study prior to the Assessment Day (Day 360 Assessment for Treatment, Day 30 Assessment for Attempt) without experiencing a primary endpoint event will be censored on the date of withdrawal. Subjects who undergo a second re-ablation procedure or a re-ablation procedure following the Blanking Period without experiencing a primary endpoint event will be censored as of the date of that re-ablation procedure. Subjects who are determined to be Severe COVID-19 Subjects during trial participation without experiencing a primary endpoint event will be censored as of the Onset Date of the condition.

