3.3 Primary Safety Endpoint

The primary safety endpoint (PSE) is the proportion of Treatment Subjects and Attempt Subjects with one or more of the following device or procedure-related Composite Serious Adverse Events (CSAEs) assessed through Day 90 following the Index Procedure / Rescheduled Index Procedure or the Re-Ablation Procedure on or prior to the Day 90 Assessment, with an Onset Date following the procedure as specified in **Table 3.3-1**.

Table 3.3-1: Primary Safety Endpoint Composite Serious Adverse Events

Composite Serious Adverse Events	Onset Date

 • Myocardial infarction • Stroke • Transient Ischemic Attack (TIA) • Peripheral or organ thromboembolism • Pulmonary edema • Unresolved phrenic nerve palsy / paresis • Vascular access complications • Heart block • Gastric motility / pyloric spasm disorders 	Day 0 – Day 7

 • Death • Cardiac tamponade / perforation • Pericarditis • Any PFA system related PFA procedure-related cardiovascular or pulmonary adverse event 	Day 0 – Day 30

 • PV stenosis • Atrio-esophageal fistula 	Day 0 – Day 90

For the analysis of the PSE, CSAEs are only defined for the following procedures that include the use of investigational devices:

- The Index Procedure / Rescheduled Index Procedure (**Section 7.7**)
- A Re-Ablation Procedure for AF, AFL or AT on or prior to the Day 90 Assessment (FARAWAVE only) (**Section 7.14**)

Device or procedure-related SAEs related to any other ablation procedure that does not include an investigational device will not be included in the analysis of the PSE, including those from Other Re-ablation Procedures (**Section 7.14.2**).

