7.14 Re-Ablation Procedures

7.14.1 Re-Ablation Procedure within the Blanking Period

For subjects undergoing a first re-ablation procedure within the Blanking Period for Detectable AF, AFL or AT, the procedure will be performed by the investigator under the procedures and data

requirements of **Section 7.7.1**, modified to assess and treat only those locations required, and including the pre- and post-procedure NIHSS.

The FARAPoint PFA Catheter will not be utilized for any re-ablation procedure. If repeat ablation is required for CTI-mediated flutter, any commercially available BSC RF catheter will be used. Such re-ablation using the methods and devices described in **Section 7.7.1** does not constitute a Treatment Failure.

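### Phase 2 censors the primary safety endpoint at any re-ablation using a commercial catheter, which does not match the procedures and events that Appendix A Section 3.3 counts

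*Combined protocol and SAP*

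**What the plan says.** **Endpoint (Appendix A 3.3).** The section states that "CSAEs are only defined for the following procedures that include the use of investigational devices". It lists the Index or Rescheduled Index Procedure and a second item, "A Re-Ablation Procedure for AF, AFL or AT on or prior to the Day 90 Assessment (FARAWAVE only" (the parenthesis closes there). It then says what is left out, in a sentence that ends by naming this endpoint: "Device or procedure-related SAEs related to any other ablation procedure that does not include an investigational device will not be included in the analysis of". Death, tamponade or perforation, pericarditis and PFA-related cardiovascular or pulmonary events count to Day 30. PV stenosis and atrio-esophageal fistula count to Day 90.

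**Catheters at re-ablation (Appendix A 7.14.1).** The first re-ablation in the Blanking Period treats only the locations that need it. On the focal catheter the section says: "The FARAPoint PFA Catheter will not be utilized for any re-ablation procedure". On repeat treatment of the isthmus it says: "If repeat ablation is required for CTI-mediated flutter, any commercially available BSC RF catheter will be used".

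**Analysis rule (Appendix A 8.1.1.3).** The rule applies to "Subjects who undergo a re-ablation procedure using a commercially available ablation catheter before the Day 90 Assessment without experiencing a primary endpoint event". Follow-up for the endpoint then stops, since each such subject "will be censored as of the date of that re-ablation procedure". Nothing is said about a session that also uses FARAWAVE, or about later events that belong to the Index Procedure.

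**Phase 1 rule (main protocol 8.1.1.3).** The trigger is different: "Subjects who undergo a second re-ablation procedure or a re-ablation procedure following the Blanking Period". A first blanking re-ablation is not a censoring event, whichever catheter is used.

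**The concern.** Section 3.3 decides what counts by asking whether the procedure an event relates to included an investigational device. Section 8.1.1.3 removes the subject from the risk set because a commercial catheter was present. The two tests give different answers in two situations.

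1. **Mixed session.** A first blanking re-ablation treats PVs or posterior wall with FARAWAVE and the CTI with RF. It includes an investigational device, yet the subject is censored that day. A stroke or tamponade on the following day would be dropped.
2. **RF-only re-ablation.** Suppose a CTI re-ablation on Day 20. An Index-related pericarditis on Day 26, or a fistula on Day 60, is within its window and relates to the Index Procedure, but it falls after the censoring date.

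In both cases the analysis loses events that the endpoint definition keeps. This endpoint is half of the success criterion, and a lower event count favours success.

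**Working it through.** **Inputs (Appendix A 8.1.1.2).** Expected rate 6%, performance goal 12%, one-sided 0.025, 245 evaluable subjects, 258 after 5% attrition, stated power 88%. The documents give no re-ablation rate.

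**The plan's own figure.** The exact binomial rule takes the largest c with P(X ≤ c | 245, 0.12) ≤ 0.025.
- c = 19: probability 0.0211. c = 20: probability 0.0351.
- Power = P(X ≤ 19 | 245, 0.06) = 0.898, against a stated 88%.
- 245 / 0.95 = 257.9, so 258.

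The stated power is reproduced to within 2 points. The sample size is not at issue.

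**Decision boundary at 258 subjects.** This uses the planned log-log limit and assumes no other censoring. With k events, S = 1 − k/n, Greenwood SE(S)/S = √[k / (n(n − k))], θ = 1.96 × that ratio / |ln S|, and upper limit = 1 − S^exp(θ).

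| k | S | SE(S)/S | θ | Upper limit | Result |
|---|---|---|---|---|---|
| 20 | 0.9225 | 0.01805 | 0.438 | 11.76% | pass |
| 21 | 0.9186 | 0.01853 | 0.428 | 12.21% | fail |

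One event is 1/258 = 0.39 percentage points. Passing at 20 or fewer has probability 0.0182 when the true rate is 12%.

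**Expected loss, narrow assumption.** Appendix A 4.1.2 expects about 80 FARAPOINT subjects. Assume 1% to 5% of them have a commercial-catheter re-ablation before the Day 90 Assessment: 0.8 to 4 subjects. Assume each carries a 6% to 12% risk of a later event that 3.3 counts.
- Low end: 0.8 × 0.06 = 0.05 events.
- High end: 4 × 0.12 = 0.48 events, or 0.48/258 = 0.19 points.
- Type I error at a true 12%, high end: P(X ≤ 20 | 258, 0.1181) = 0.0225, still under 0.025.

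**Expected loss, wide assumption.** Assume 1% to 10% of all 258 subjects are affected, with a 3% to 12% later risk.
- Lost events: 258 × 0.01 × 0.03 = 0.08, up to 258 × 0.10 × 0.12 = 3.10.
- Type I error: 0.019 to 0.065. It passes 0.025 when the product of the two assumptions reaches about 0.3 points (5% × 6% gives 0.0255).

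**Whether another analysis covers this.** The tipping-point analysis in Appendix A 8.3.3.1 addresses subjects who exit the study before the Day 90 Assessment. Subjects censored at re-ablation stay in follow-up, so it does not reach them.

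**The case against.** **The qualifier in 3.3.** If the FARAWAVE-only parenthesis means FARAWAVE was the sole catheter, 3.3 and 8.1.1.3 agree on mixed sessions. That reading is available. The other reading, that it excludes FARAPOINT, is better supported: FARAPOINT is barred from re-ablation, and the exclusion sentence in the same section reaches only procedures without an investigational device. It remains an ambiguity, and the mixed-session point depends on how it is resolved.

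**The censoring clause.** It has no time limit. Read literally, a subject with a later Index-related fistula has experienced an endpoint event and is not among those censored. The ordinary reading is no event before the re-ablation, but the text does not say so. The separate Phase 2 SAP that Appendix A cites may settle the programming; that cannot be checked here.

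**Phase 1.** A reader might infer that losing later Index-related events is peculiar to Phase 2. It is not. Phase 1 also censors, at a second or post-blanking re-ablation, while counting PV stenosis and fistula to the Day 360 Assessment. The real difference is the first blanking re-ablation with a commercial catheter.

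**Size.** Appendix A 8.1.1 says all meta-analysis events had onset before Day 30, so few late events are expected. Kaplan-Meier censoring removes a subject from the risk set rather than scoring a success, and an event on the procedure date would usually still count. At a true 6% rate, exactly 21 events in 258 has a probability of about 3.5%. All SAEs also remain visible in the additional safety endpoints (Appendix A 3.5.1). This stands: the effect is probably small.

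**Informative censoring.** A reader might infer that those censored have the most extensive recurrence and longest repeat procedures. The documents do not say so, and it does not describe an RF-only CTI re-ablation.

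**Conclusion.** The mismatch is real, subject to two wording questions. The mixed-session loss holds if the qualifier in 3.3 excludes FARAPOINT rather than requiring FARAWAVE alone. The loss of later Index-related events holds if the censoring clause means no event before the re-ablation. Both are the more natural readings, and both wordings should be reconciled.

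On 1 to 4 censored subjects and a 6% to 12% later risk, the expected loss is under about 0.5 events. The re-ablation rate and the later risk are both assumptions. A reader might infer that the rule puts the 2.5% error level in doubt. The narrow range does not support that, and the wide range reaches it only under rates for which the documents give no basis. What remains is direction: the rule can only lower the number of events observed, and one event matters at 20 versus 21 of 258. The analysis rule should be aligned with the endpoint definition before the analysis.

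**What to change.** 1. In Appendix A 8.1.1.3, state that a first blanking re-ablation that includes FARAWAVE is not a censoring event and that its CSAEs count, even if a commercial catheter is also used.
2. In Appendix A 3.3, reword the FARAWAVE-only qualifier so that its meaning is explicit. In 8.1.1.3, say whether the no-event condition refers to the time before the re-ablation or to the whole endpoint period.
3. For re-ablations with no investigational device, count later CSAEs that the CEC attributes to the Index Procedure or an earlier FARAWAVE re-ablation, at minimum as a prespecified sensitivity analysis.
4. Ask the CEC to record which procedure each such event relates to. Main protocol 19.2 has it judge relation to the ablation procedure and/or catheter, but does not require it to separate an Index Procedure from a later RF procedure.

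The cost is a short text change in two sections, the matching SAP text, and one more attribution field on the CEC form. The sample size stays at 245 evaluable and 258 enrolled. The observed event rate may be slightly higher.

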8.1.2 Primary Effectiveness Endpoint

The Primary Effectiveness Endpoint (PEE) is defined in **Section 3.4**. The definition of the PEE remains consistent with the ADVANTAGE AF Phase 1 PEE, apart from the definition of Detectable AF, AFL, or AT (Section 23.2), which has been adjusted for recurrence monitoring using an ICM in place of standard recurrence monitoring methods.

The observed one-year treatment success based on standard non-continuous monitoring methods (12-lead ECG at each follow-up visit, 24-hour Holter every 6 months, regular or scheduled event monitor transmissions, and symptom-driven event monitoring) is expected to be higher than what could be observed from an ICM, given its capability of continuously monitoring the heart rhythm during the entire period of observation. Based on a comparison with data obtained from the CIRCA-DOSE trial which included subjects with paroxysmal AF, it has been estimated that an arrhythmia recurrence assessment based on ECG, Holter monitoring and symptomatic episodes captured from event monitors would lead only to 40.9% sensitivity and 65.3% negative predictive value when compared to an ICM¹⁹.

While the value in implementing continuous arrhythmia monitoring post AF ablation is well accepted, to date no standards are defined for determining one-year treatment success when using ICMs for arrhythmia monitoring, leading to inconsistency in methodology including but not limited to, different episode duration cutoffs, variable ICM programming, and inconsistency in symptom-driven monitoring. The limited number of studies assessing post ablation outcomes with ICM to date report variable one-year arrhythmia recurrence rates ranging from 27% to 64%²²⁻³². These studies use different arrhythmia duration criteria (from >30 seconds to 24 hours), different timelines for ICM insertion in respect to ablation procedure, and different endpoint definitions (recurrence vs burden). Accordingly, results obtained from different ablation studies using ICM are heterogeneous and not comparable, so they cannot be analyzed collectively to form a hypothesis for the ADVANTAGE Phase 2 PEE based on continuous monitoring.

Alternatively, non-continuous monitoring will be simulated using ICM data to allow for robust hypothesis generation. Time periods representing bi-monthly event monitor transmissions and 24-hour Holter monitor recordings will be selected and reviewed for LUX-Dx detected AF, AFL, and AT. The duration and frequency of the time periods will mimic the use of event monitors and Holter monitors in ADVANTAGE Phase 1, which is consistent with recommendations set by the 2017 HRS consensus statement on AF ablation for monitoring recurrence in persistent atrial fibrillation patients. 12-lead ECGs will also be used for recurrence monitoring with no change to their contribution to Detectable AF, AFL, or AT compared to Phase 1.

As such, PEE assumptions remain identical to ADVANTAGE Phase 1 (**Table 8.1-3**). Derivation of the expected rate is described in Phase 1 Section 8.1.2.

A PEE performance goal of 40% has been chosen as it preserves the standard provided by the 2017 HRS/EHRA/ECAS Expert Consensus document on the minimum chronic acceptable success rate for persistent AF at 12-month follow-up:²⁰

“If minimum chronic success rate is selected as an objective effectiveness endpoint for a clinical trial, we recommend that the minimum chronic acceptable success rate for persistent AF at 12-month follow-up is 40%.”

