7.11 Day 90 Assessment

Type of Assessment: In-person at investigational site required; remote only for documented COVID-19 related disruption.
Window: 90 ± 14 Days
If a COVID-19-related disruption prevents an in-person assessment within window: 
As much data as possible may be collected remotely.The absence of a 12-lead ECG during a remote assessment is not a protocol deviation.If a radiologic examination is required due to prior diminished phrenic nerve response, an inspiration / expiration chest X-ray (CXR) performed in-person or at another healthcare site may be substituted.
AAD Treatment: During the Blanking Period the subject should be assessed for AAD continuation. At Investigator discretion, Class I / III AADs may be stopped to allow assessment of the subject's potential for off-drug freedom from recurrent AF, AFL, or AT. Subjects who require continued AAD treatment may be continued; preferably with a Failed AAD . Using a Non-Failed AAD or amiodarone would create an unnecessary Treatment Failure.

Subjects will be assessed at Day 90 ± 14 days following the Index Procedure / Rescheduled Index Procedure. Study data will be collected at the Day 90 Assessment including but not limited to:

- Adverse events
- Data regarding the use, changes in or discontinuation of anticoagulation, rate control and / or AADs
- Recurrent arrhythmia, cardioversions, ablations, or hospital admissions since last assessment
- Site staff will confirm ICM programming and successful LATITUDE Clarity transmissions since last assessment
 - Assess for any recurrence of AF/AFL/AT
 - Any reported AFL recurrence will require a 12-lead ECG for ACL adjudication
 - Confirm ICM programming parameters
 - Any programming outside of the defined nominal parameters (Section 7.6) prior to a confirmed recurrence of Detectable AF, AT or AFL must be entered into the EDC and justification provided.
 - ICM may be reprogrammed, as needed, to facilitate appropriate arrhythmia identification and investigator notification after the subject experiences a confirmed recurrence of Detectable AF, AT or AFL.
- Cardiac rhythm as determined by a 12-lead ECG at the time of the assessment (in-person assessment only). All 12-lead ECGs for Treatment Subjects will be provided to the Arrhythmia Core Laboratory (ACL).

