7.18 Source Documents

It is preferable that original source documents are maintained, when available. In lieu of original source documents, certified copies are required to be maintained. A certified copy is a copy (irrespective of the type of media used) of the original record that has been verified (i.e., by a dated signature or by generation through a validated process) to have the same information, including data that describe the

context, content, and structure, as the original. Source documentation includes but is not limited to those items noted in **Table 7.18-1** below.

Table 7.18-1: Source Documentation Requirements

Requirement	Disposition
Screening and enrollment log	Retain at Center
Informed consent documentation process	Retain at Center
Medical history documents pertaining to eligibility criteria	Retain at Center
Documentation of demographics data	Retain at Center
Pregnancy testing, if applicable	Retain at Center
Required laboratory testing	Retain at Center
Cardiovascular / pulmonary examination	Retain at Center
Procedural Medications Administered, AADs, and Anticoagulation Medication Regimen and Changes	Retain at Center
Medical history	Retain at Center
Quality of Life Instruments (AFEQT and EQ-5D-3L)	Retain at Center
NIH Stroke Scale Assessments	Retain original at center and submit copies and copies of all associated source documents if an increase in scale is observed from baseline
If determined necessary, neurological consultation and brain MRI (DW-MRI)	Retain originals at center and submit copies of all source documents and copy of complete scan to BSC
Baseline cardiac imaging and any required follow-up imaging	Retain at Center
LUX-Dx insertion details and arrhythmia recurrence recordings	Retain insertion data at Center and Upload recurrence data to BSC EDC
12-Lead ECGs data including ongoing rhythm	Retain at Center Submit copies of the ECGs collected at Day 90 and Day 360 Follow up, from LUX-Dx detected AFL recurrence, and Unscheduled visits when applicable to the ACL.
Post-ablation electrograms showing entrance block for each treated PV	Retain at Center (Submit to BSC if Rhythmia)
Post-ablation electrogram documentation demonstrating PWI	Retain at Center (Submit to BSC if Rhythmia)
Post-ablation electrograms showing bidirectional isthmus block (CTI ablations only)	Retain at Center (Submit to BSC if Rhythmia)
Recording lab logs, showing PV entrance block, PW isolation and CTI BDB (if applicable)	Retain at Center

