8.1.2.3 Statistical Methods

The proportion of LUX-Dx monitored Treatment Subjects with PersAF Treatment Success through the Day 360 Assessment will be estimated using the Kaplan Meier method. The 97.5% one-sided lower confidence limit of the observed Treatment Success rate will be compared to the performance goal of 40%. If the lower confidence limit is greater than the performance goal, the null hypothesis will be rejected. The confidence limit will be calculated as the pointwise confidence limit using log-log methodology.

Each LUX-Dx monitored Treatment subject will be classified as Treatment Success (event-free) or Treatment Failure (PEE event). Subjects must have an active LUX-Dx device with established LATITUDE Clarity connection by the end of the effectiveness evaluation period to be included in PEE analysis. Subjects who withdraw or die from the study prior to the Day 360 Assessment, without experiencing a PEE event, will be censored on the date of withdrawal or death. Subjects who are determined to be Severe COVID-19 Subjects during trial participation without experiencing a PEE event will be censored as of the Onset Date of the condition.

LUX-Dx data will be used to simulate intermittent arrhythmia monitoring methods consistent with the methods used in ADVANTAGE AF Phase 1. Bi-monthly (asymptomatic) event monitor transmissions will be simulated by randomly selecting LUX-Dx data from two, 2-minute time windows every 30 days starting on the date of the Day 90 assessment. Each 30-day interval contains 2,592,000 seconds from which 2 seconds will be selected via simple random sampling and used as the starting point for a 2-minute (120 second) window. The first 2-minute window will be removed prior to sampling the second 2-minute window to avoid overlapping windows. The sampling seed will equal the date of the first subject enrollment..

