Only 2-minute windows occurring after the blanking period will be used for analysis. Thirty-day intervals will repeat until an interval contains an in-window Day 360 Assessment, Day 390, or subjects' End of Study date, whichever occurs first. In the final 30-day interval, only 2-minute windows occurring on or prior to the in-window Day 360 Assessment, Day 390, or subjects' End of Study date, will be used for analysis. If a 2-minute window occurs on the same day as a scheduled study visit (Day 180 or Day 360 Assessment) or on the same day as the simulated Holter patch, then a new 2-minute window will be randomly selected to avoid overlapping with the 12-lead ECG recording and simulated Holter patch recording.

Twenty-four (24) hour Holter patches will be simulated by selecting LUX-Dx data from the day before the Day 180 and Day 360 Assessments. The day before was selected to avoid overlapping with the 12-Lead ECG recordings from each visit. For subjects that had a missed visit for the Day 180 or Day 360 assessment, the last day of the subject's visit window will be used for the simulated Holter patch.

Recurrence will be defined as a stored LUX-Dx AT or AF episode that is adjudicated as containing at least 30 seconds of atrial arrhythmia and that overlaps a simulated window by any amount. Additionally, all LUX-Dx recorded symptomatic episodes and all 12-lead ECGs will be assessed for AF, AFL, or AT recurrence as defined in Protocol Section 23.2.

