8.3.6 Treatment Success Rate by Arrhythmia Detection Method

PersAF Treatment Success rates through Day 360 Assessment will be compared between ADVANTAGE AF Phase 1 and Phase 2 Treatment Subjects to assess differences in chronic success when using the continuous monitoring from an ICM to simulate non-continuous monitoring for recurrence compared to standard assessment based on true Holter monitoring and periodic

transmissions from event monitors. A propensity score analysis utilizing inverse probability of treatment weights (IPTW) will be used to estimate the absolute difference in PersAF Treatment Success rates between detection groups (ICM vs. Standard) while minimizing the effects of confounding variables. Details of this analysis will be included in the Appendix A of the ADVANTAGE AF SAP.

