Detectable AF, AFL, or AT	
Detectable AF, AFL or AT is an episode of AF, AFL or AT which:
 
 • Is recorded for review on a LUX-Dx ICM and meets any of the following criteria: 
 ○ Adjudicated symptomatic (patient initiated) recording that contains ≥ 30 seconds of continuous atrial arrhythmia. ○ Adjudicated AF or AT episode captured by LUX-Dx that contains at least 30 seconds of atrial arrhythmia and overlaps a simulated bi-monthly, 2 minute event monitor transmission period. ○ Adjudicated AF or AT episode captured by LUX-Dx that contains at least 30 seconds of atrial arrhythmia and overlaps a simulated 24 hour holter period occurring the day before the Day 180 and Day 360 Assessments (or last day of respective visit window if visit(s) is missed)⁸. • Continuous AF, AFL or AT for the entirety of a 12 lead ECG if the continuous interpretable signal is 10 seconds or longer • Exclusions: 
 ○ CTI isthmus-dependent AFL if the subject did not have a CTI ablation with the FARAPoint PFA Catheter ○ Arrhythmias recorded on other devices, including implantable monitors and consumer wearables, not specified in the ADVANTAGE AF Study procedures
Failed AAD	
Failed AADs include any and all Class I / III AAD determined at the time of enrollment to have been failed for effectiveness or intolerance. Failed AADs do not include Class I / III AADs determined at the time of enrollment solely to be contraindicated.
 
Failed AADs must be established as part of the Baseline Assessment for agent, type of failure (arrhythmia recurrence or AAD intolerance) and the maximum failed dose (the total daily dose at which such failure occurred).

Intent Subjects	
Intent Subjects are defined in Section 6.6.3 of the ADVANTAGE Phase 1 Protocol.

Non-Failed AAD	
A Non-Failed AAD is:
 
 • Any Class I / III AAD not established at the Baseline Assessment as a Failed AAD • Any Failed AAD used after Day 90 at a daily dose exceeding the maximum failed dose established at the Baseline Assessment

⁸ Day prior to the Day 180 and Day 360 visits was selected to prevent overlap in the rhythm captured by the visit-required 12-lead ECG.

Term	Definition
Persistent atrial fibrillation	PersAF is defined as continuous AF that is sustained beyond 7 days, but not greater than 12 months duration.

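### The Phase 2 effectiveness endpoint counts 12-lead ECGs ordered because of LUX-Dx detected flutter, a route to failure that Phase 1 lacked; it biases the Section 8.3.6 comparison and should be isolated in one added analysis

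*Combined protocol and SAP*

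**What the plan says.** All references are to Appendix A (Phase 2) unless marked otherwise.

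- **Aim.** Section 8.1.2.3: "LUX-Dx data will be used to simulate intermittent arrhythmia monitoring methods consistent with the methods used in ADVANTAGE AF Phase 1". Two 2-minute windows per 30 days stand in for event-monitor transmissions, and the day before the Day 180 and Day 360 visits stands in for each Holter.
- **Role of ECGs.** Section 8.1.2 says they are "used for recurrence monitoring with no change to their contribution to Detectable AF, AFL, or AT compared to Phase 1", and then carries over the Phase 1 planning assumptions (Table 8.1-3: 55% expected, 40% goal, 122 evaluable, 136 with attrition).
- **Which ECGs count.** Section 8.1.2.3: "all LUX-Dx recorded symptomatic episodes and all 12-lead ECGs will be assessed for AF, AFL, or AT recurrence". The criterion in Section 23.2 is "Continuous AF, AFL or AT for the entirety of a 12 lead ECG if the continuous interpretable signal is 10 seconds or longer". It requires no overlap with a simulated window.
- **What prompts an ECG.** At Day 30, 90, 180, 360 and unscheduled contacts (Sections 7.10 to 7.13 and 7.15), site staff check LUX-Dx transmissions for recurrence, and "Any reported AFL recurrence will require a 12-lead ECG for ACL adjudication". Table 7.18-1 names the trigger directly: ECGs "from LUX-Dx detected AFL recurrence, and Unscheduled visits when applicable to the ACL" are to be submitted.
- **Phase 1.** An active implanted monitor at ablation was an exclusion (main protocol, Table 5.3-1, item 2c), and recordings from implantable monitors outside the study procedures did not count (main protocol, Section 23.2).
- **Later use.** Section 8.3.6 compares success between the phases, with Phase 2 described as "using the continuous monitoring from an ICM to simulate non-continuous monitoring for recurrence".

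**The concern.** The simulation is meant to discard what only continuous monitoring sees. A LUX-Dx AFL episode that falls in no simulated window and was not patient-initiated is not a recurrence. If the site sees that episode, obtains the required 12-lead, and the flutter is still present, the ECG is a recurrence. Continuous monitoring then enters the endpoint by a second route.

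Two things are at stake. First, the expected rate of 55% comes from monitoring that had no such trigger. Second, Section 8.3.6 is meant to compare simulated with true intermittent monitoring, but ICM-prompted ECGs arise in Phase 2 only, so the estimate mixes the quality of the simulation with additional ECG testing. Weighting on subject characteristics cannot remove this, because the trigger belongs to the phase and not to the subject. None of the analyses in 8.3.3.1 to 8.3.3.7 separates these ECGs. Section 8.3.3.6 deals with the opposite problem, AT/AFL that goes undetected.

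**Working it through.** **1. The plan's own figure.** Exact binomial, one-sided 0.025, goal 40%, expected 55%, n = 122 (Table 8.1-3). The smallest success count r with P(X ≥ r | 0.40) ≤ 0.025 is r = 60, with attained alpha 0.0248. Power is P(X ≥ 60 | 0.55) = 0.916, against 90% stated. Attrition: 122 / 0.90 = 135.6, rounded up to 136. The plan reproduces; the issue is the endpoint, not the arithmetic.

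**2. Where an ICM-prompted ECG can change a subject's outcome.**

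| Contact | 12-lead already planned in Phase 2? | Added route to failure |
|---|---|---|
| Day 30 (window 30 to 37) | No | None: inside the blanking period |
| Day 90, Day 360 | Yes, as in Phase 1 | Little: arrhythmia still present would be caught anyway |
| Day 180 (remote) | None in Table 7.2-1 | Yes, if AFL is reported |
| Unscheduled, on site | Yes, as in Phase 1 | Only where LUX-Dx data led to the visit |

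The clear extra route is AFL found at the remote Day 180 contact or between visits. The required ECG covers AFL only. AF and AT alerts can lead to an ECG only indirectly, through an unscheduled visit or the evaluation of a possible arrhythmia. CTI-dependent AFL does not count unless the subject had CTI ablation with FARAPOINT, expected in about 30% (Section 4.1.2).

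**3. Upper illustration of size.**

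Inputs: negative predictive value (NPV) of intermittent monitoring against an ICM, 65.3% (Section 8.1.2, from a paroxysmal AF trial); planned success 55%; an assumed share f of ICM-only recurrences that turn into ECG failures. No document gives f; I use 10% to 30%.

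- Share of intermittent-monitoring successes with an ICM-detectable recurrence: 1 − 0.653 = 0.347.
- As a share of all subjects: 0.55 × 0.347 = 19.1%.
- Success with prompted ECGs counted: p = 0.55 × (1 − 0.347f).

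Power is exact, with critical count 60 at n = 122 and 109 at n = 232. The latter is 258 × 0.90, assuming all 258 Treatment Subjects are LUX-Dx monitored (8.2.1 analyses all who are).

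| f | Success | Fall (points) | Power, n = 122 | Power, n = 232 |
|---|---|---|---|---|
| 0 | 55.0% | 0 | 0.92 | 0.99 |
| 10% | 53.1% | 1.9 | 0.83 | 0.97 |
| 20% | 51.2% | 3.8 | 0.70 | 0.91 |
| 30% | 49.3% | 5.7 | 0.54 | 0.78 |

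This is an upper illustration for two reasons. The 19.1% covers every ICM-only recurrence, whereas the required ECG covers AFL. And the comparator behind the 65.3% is described as ECG, Holter and symptomatic event-monitor episodes, without the scheduled transmissions that Phase 2 also simulates, so the missed share is probably smaller.

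**The case against.** **The sentence in 8.1.2 is right about the criterion.** The 12-lead rule (arrhythmia throughout, at least 10 seconds) is the same in both phases, and both accept ECGs submitted while a possible arrhythmia is being evaluated. This stands. What does not follow is that the planning assumptions are identical, since that also depends on which ECGs are taken. Nor did Phase 1 have a parallel: a qualifying event-monitor or Holter recurrence already counted there, so an ECG that it prompted added nothing.

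**The ECG has its own purpose.** It supports core laboratory adjudication, and CTI-mediated AFL must be confirmed on a 12-lead (3.5.2). This is a good reason to obtain it, but it does not settle whether it should count in a simulated intermittent endpoint.

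**A Day 180 ECG may be routine after all.** Section 8.1.2.3 and the footnote to the Detectable AF definition write as though a 12-lead is recorded at Day 180, while Table 7.2-1 and Section 7.12 schedule none. If one is done routinely, the Day 180 route shrinks and the between-visit route remains.

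**The rest may be in the SAP.** Details of 8.3.6 and of LUX-Dx adjudication are deferred there, so handling by ECG source cannot be ruled out. Nothing in the text available provides it.

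**Stronger readings that a reader might infer:**

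- *Everything the LUX-Dx detects returns to the endpoint.* Not supported: the required ECG is for AFL, and the arrhythmia must still be present on it.
- *The loss is 2.8 to 8.4 points.* This comes from solving the NPV and the 40.9% sensitivity (assuming perfect specificity) for an ICM recurrence rate of 47.3%, of which 0.591 × 47.3% = 28.0% of subjects are missed, and converting 10% to 30% of these. But that solution implies intermittent success of 1 − 0.409 × 0.473 = 80.6%, which is inconsistent with subtracting the result from 55%.
- *The primary test is compromised.* Not supported: added failures cannot inflate type I error against 40%.

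**Conclusion.** The point holds in a limited form. Section 8.1.2 justifies the Phase 1 assumptions by equivalent monitoring, while 8.1.2.3 and 23.2 count ECGs that exist only because an implanted monitor showed AFL. For the primary test the effect is conservative, and any loss of power is the sponsor's risk. With about 232 evaluable subjects, power stays at 0.78 or above across the illustrated range. That range rests on an assumed 10% to 30% conversion, paroxysmal AF data and a share not restricted to AFL; the true effect may be small.

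The more important consequence is for 8.3.6, which as written attributes ICM-driven ECG failures to simulated monitoring and so leans toward lower Phase 2 success. That comparison is supportive and not a success criterion, so I class this as a cheap improvement, not a defect that threatens the trial's conclusion.

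**What to change.** 1. On the ECG and Unscheduled Assessment CRFs, record why each post-blanking 12-lead was done: scheduled, symptoms or other clinical reason, or LUX-Dx review or alert.
2. Leave the primary test unchanged, with all 12-leads counting.
3. Add to 8.3.3 a repeat of the primary effectiveness analysis in which a 12-lead obtained only because of LUX-Dx data does not count, unless the episode also meets the simulated-window or symptomatic rule.
4. Report 8.3.6 with that version beside the all-ECG version.
5. Reword 8.1.2 to say that the ECG criterion is the same as in Phase 1 but that ECG ascertainment is not.
6. Reconcile Table 7.2-1 and Section 7.12 with 8.1.2.3 on whether a Day 180 12-lead is planned.

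Cost: one CRF field, one additional analysis, a second column in 8.3.6 and a few sentences. The reason for an ECG is hard to reconstruct later, so it should be captured as data are collected, and any ECGs already taken would need it back-filled from source. The downside is that the added figure can only favour the sponsor, so it must stay secondary. If prompted ECGs prove rare, the analysis will show that and support the equivalence claim.
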